6.3.1 Primary Effectiveness Variable

Progression of disease at 2 years (POD24), defined as the time from the date of treatment initiation with Obinutuzumab until the first documented progression of disease or death due to disease progression, whichever occurs first, within 24 months from the start of treatment with Obinutuzumab. Patients who have no disease progression and have not died due to disease progression or who are lost to follow-up at the time of analysis will be censored at the date of last tumor assessment where no progression was documented or the last date of follow-up for disease, whichever is last. Patients without post-baseline tumor assessments will be censored at the time of their baseline visit unless death due to disease progression occurs prior to their first scheduled tumor assessment. Patients who die for reasons not related to the disease progression within 24 months from the treatment start with Obinutuzumab will be excluded from the statistical analysis of the endpoint.

Moreover, the POD24 will be also analyzed as binary variables. Number and percentage of patients with its 95% confidence interval for POD24 will be calculated.

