6.4.2 Data Collected during the Observation Period

During therapy with Obinutuzumab, laboratory assessments are routinely performed in accordance with current guidelines and local standard of care. When performed during the observational period, available results that represent an adverse event in accordance to CTCAE vs. 5, relevant symptom/signal of an event or abnormal laboratory finding that results in a change of the treatment in study will be documented in the eCRF. Most data will be documented during the treatment period when the respective assessments are usually performed according to standard of care. The proposed assessments and suggested timings for assessments in the protocol/observational plan are not mandatory. It is up to the treating physician to perform and document the assessments as performed in the real clinical setting.

In the routine care setting, patients are seen regularly by their treating physicians either for treatment or for regular assessment after treatment. Thus, no study-specific visits or evaluations are required by this protocol.

Tumor assessments collected in eCRF will comprise the following periods as available:

- Baseline tumor assessment
- During induction:
 - Mid induction: tumor assessment performed between cycle 2 and cycle 4 after the start of treatments
 - End induction: tumor assessment performed at the day of cycle 6 /8 (or when induction is early discontinued) until 2 month later
- After induction treatment:
 - 1 year after the start of treatment (from 10 to 14 months after the start of treatment)

- 2 years after the start of treatment (from 22 to 26 months after the start of treatment)
- 3 years after the start of treatment (from 34 to 40 months after the start of treatment)
- 1 year after end of maintenance as applicable
- Any tumor assessment, and the method used that shows disease progression, CR or CRu during induction or maintenance.

The lack of tumor assessments in those periods are not a protocol deviation as clinical practice should be followed.

Since the enrolment of patients into the study will occur after the treatment has already started (Patients included should have performed at least 2 cycles of induction treatment with Obinutuzumab but no later than the completion of 1 year of the treatment with Obinutuzumab), a retrospective data collection is expected.

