^j Response will be collected at mid of the induction (between 10 and 14 weeks after the start of treatments), end of the induction (at the day of cycle 6 until 1 month later) during maintenance (1 year after the start of treatment, i.e. from 10 to 14 months after the start of treatment; 2 years after the start of treatment, i.e. from 22 to 26 months after the start of treatment; 3 years after the start of treatment, i.e. from 34 to 38 months after the start of treatment), at the end of maintenance and at Follow-up as per clinical practice, as well as at any tumor assessment that shows disease progression, CR or CRu during induction or maintenance. The assessment of tumor response will be based on standard Cheson criteria and the Deauville 5-point scale (Appendix 6) (Younes et al. 2017).

^k All adverse events data available in medical records after start of the treatment should be reported until 185 days after the last obinutuzumab dose or until starting a new anti-cancer therapy (whichever occurs first). After this period AEs that are believed to be related to prior study drug treatment will be collected.

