2.3 PRIMARY OUTCOME MEASURES

Progression of disease at 2 years (POD24), defined as the time from the date of treatment initiation with Obinutuzumab until the first documented progression of disease

or death due to disease progression, whichever occurs first, within 24 months from the start of treatment with Obinutuzumab. Patients who have no disease progression and have not died due to disease progression or who are lost to follow-up at the time of analysis will be censored at the date of last tumor assessment where no progression was documented or the last date of follow-up for disease, whichever is last. Patients without post-baseline tumor assessments will be censored at the time of their baseline visit unless death due to disease progression occurs prior to their first scheduled tumor assessment. Patients who die for reasons not related to the disease progression within 24 months from the treatment start with Obinutuzumab will be excluded from the statistical analysis of the endpoint.

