3.2.1 Primary Outcome Measures

The primary endpoint is progression of disease at 2 years (POD24).

POD24 will be analyzed according to the survival analysis methods. The quartiles with their 95% confidence interval (estimated using Kaplan-Meier methods and Greenwood's formula) will be presented. Kaplan-Meier plots with a 95% CI will be prepared. Estimates for the survivor function will be obtained by the Kaplan-Meier approach.

Moreover, the POD24 will be analyzed as binary variable. Number and percentage of patients with its 95% CI for POD24 will be calculated.

Logistic regression analysis will be performed to assess which variables are predictive of POD24. To identify factors associated with POD24, logistic regression analysis will be performed with backwards selection (removing factors with $P > 0.05$). Univariable associations between factors and POD24 will be calculated by using the Chi-square test.

In the analysis of POD24 will be excluded patients who die within 24 months from the treatment start with Obinutuzumab for reasons not related to the disease progression.

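### The 2-year tumor assessment may fall at months 22–26 but POD24 stops at month 24, so scan date alone can decide whether a progression counts; supporting analyses are needed

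*Protocol*

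**What the plan says.** Protocol 6.3.1 defines the primary event as "first documented progression of disease or death due to disease progression, whichever occurs first, within 24 months from the start of treatment with Obinutuzumab". SAP 2.3 uses the same limit, "whichever occurs first, within 24 months from the start of treatment with Obinutuzumab". Neither gives a tolerance around month 24. SAP 3.2.1 analyses POD24 by Kaplan-Meier and also as a proportion: "Moreover, the POD24 will be analyzed as binary variable", and "Number and percentage of patients with its 95% CI for POD24 will be calculated".

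Protocol Appendix 2, note j, collects response at "2 years after the start of treatment, i.e. from 22 to 26 months after the start of treatment". Protocol 6.4.2 and SAP Appendix 1, note j, give the same window. The preceding yearly window is months 10–14.

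These windows are collection periods for routine data. Protocol 6.4.2 requires no study visit or scan and does not treat a missing scan as a deviation. It also collects "Any tumor assessment, and the method used that shows disease progression, CR or CRu during induction or maintenance".

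No section says how to classify a progression first seen at an in-window scan after month 24. SAP 3.4 plans no sensitivity analysis. The bias investigations announced in Protocol 6.7.1 do not reappear in the SAP, and scan timing is not among the limitations in Protocol 6.9 or SAP 3.7.

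**The concern.** Half of the accepted window lies beyond the endpoint's cut-off. Progression is dated by documentation, and a documentation date cannot precede onset. A 2-year scan after month 24 can therefore only move a true month-24 progressor out of the event count, never add one.

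The precision of the POD24 proportion is what justifies the sample size (Protocol 6.7.5, SAP 2.6). POD24 is also the outcome of a backward-selected logistic model (SAP 3.2.1), the grouping variable in the analysis of early progression and OS (SAP 3.2.2), and one of the measures used to judge the effect of maintenance delays (SAP 3.5). If scan dates differ systematically between the groups compared, part of any POD24 difference could come from scan timing.

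**Working it through.** **The plan's own figure.** For 13% of 300, x = 39. The exact Clopper-Pearson limits are 9.41% and 17.34%, so the width is 7.93 and the half-width 3.97. The plan states 9.4 to 17.3, 7.9 and 3.95 (half of the rounded width). The figure reproduces.

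**Inputs from the documents.** Cut-off at month 24; yearly windows at months 10–14 and 22–26; expected POD24 13%; n = 300.

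**Assumptions not in the documents.** Constant progression hazard; scan dates uniform within each window; no dropout; a share s of progressions found only by scan and the rest dated at onset; imaging either yearly only or with one further routine scan at months 16–20.

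**One patient.** If onset falls after the previous scan and by month 22, and only the 2-year scan can find it, the chance of being counted is (24 − 22)/4 = 0.50. For onset at month t between 22 and 24 it is (24 − t)/4: 0.25 at month 23 and 0.125 at month 23.5.

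**Expected rate.** Hazard λ = −ln(0.87)/24 = 0.00580 per month, and F(t) = 1 − exp(−λt), so F(24) = 13.00%. The average of F is 6.72% over months 10–14, 9.92% over months 16–20, 12.49% over months 22–24 and 13.50% over months 24–26.

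Among progressions found only by scan:
- 2-year scan after month 24 (probability ½): everything since the previous scan is missed. This is 13.00 − 6.72 = 6.28 points with yearly scans, or 13.00 − 9.92 = 3.08 points with the extra scan.
- 2-year scan before month 24 (probability ½): only onset between the scan and month 24 is missed, 13.00 − 12.49 = 0.51 points.

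The mean loss m is ½ × 6.28 + ½ × 0.51 = 3.39 points with yearly scans, and ½ × 3.08 + ½ × 0.51 = 1.80 points with the extra scan. The reported rate is 13.00 − s × m. Coverage is the binomial probability, at that rate with n = 300, of the counts whose Clopper-Pearson interval contains 13% (x = 28 to 51). It is 96% when nothing is lost.

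| Found only by scan (s) | Extra scan at months 16–20: rate (coverage) | Yearly scans only: rate (coverage) |
|---|---|---|
| 20% | 12.64% (96%) | 12.32% (95%) |
| 50% | 12.10% (94%) | 11.30% (88%) |
| 80% | 11.56% (90%) | 10.29% (73%) |

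**Extreme contrast.** Take yearly scans, s = 50%, one group all scanned before month 24 and another all scanned after it. The rates are 13.00 − 0.5 × 0.51 = 12.75% and 13.00 − 0.5 × 6.28 = 9.86%. The odds ratio is (0.1275/0.8725)/(0.0986/0.9014) = 1.34 with no true difference.

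**Counting what the 2-year scan finds.** If progression first documented at the 2-year assessment is counted, the loss from late scans disappears. What remains is a loss of s × ½ × 0.51 and a gain, from onset in months 24–26, of s × ½ × (13.50 − 13.00). Each is about 0.25s points, so they nearly cancel and the rate returns to about 13.0%. The gain is 0.2 points at s = 80%. The balance depends on scan dates being symmetric about month 24.

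**The case against.** The strongest reply is that the study mandates no scan. A reader might infer from the windows that nothing is assessed between months 14 and 22. The documents do not support that: any assessment showing progression during induction or maintenance is collected with its own date, maintenance runs to about month 30, and data are collected about every 3–6 months after treatment stops. This stands, and it is why the milder column belongs beside the yearly-only one. It does not remove the problem, because a progression first found in months 24–26 keeps its late date.

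A reader might also infer that the reported POD24 will be too low overall, by a known amount. That goes too far. The loss is measured against unobserved onset, while the endpoint is defined by documentation. Protocol 6.7.5 gives no source for the 13%, and if it is itself a documented rate, the gap to it is overstated. Excluding deaths unrelated to progression pushes the rate up: if 1% to 3% of patients die this way (assumed), 13% becomes 0.13/0.99 = 13.1% to 0.13/0.97 = 13.4%. Net bias is not established when the scan-related loss is small.

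The same reasoning might be extended to 3-year PFS. Protocol Appendix 2 names an end-of-maintenance assessment, about month 30, and PFS includes deaths, which do not depend on scans. No PFS figure is offered here.

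Finally, nothing in the documents suggests that backbone or region separates patients into early and late scanning, so the odds ratio of about 1.3 shows only an extreme case. The study is exploratory and tests no formal hypothesis.

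**Conclusion.** The mismatch is real, and nothing in the plan addresses it. For this mechanism alone, and relative to true progression by month 24, the direction is certain: downward, in both the proportion and the Kaplan-Meier estimate. The size is not known. Under the stated assumptions it runs from about 0.4 points (20% found only by scan, with an extra routine scan) to 2.7 points (80%, yearly scans only), against a planned precision of 3.95 points. Coverage of 13% runs from about 96% down to about 73%; the lowest values need yearly-only imaging, which the documents neither state nor require.

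This does not justify redefining the primary event. A rule reaching to month 26 would count progressions documented after the 24 months in the endpoint's name, and it would still classify some patients by scan date. The case is for supporting analyses.

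**What to change.** Keep the strict 24-month definition as primary. In SAP 3.2.1 and 3.4, replace the statement that no sensitivity analysis is planned with two supporting analyses of POD24:

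1. The 24-month estimate with progression treated as interval-censored between the last progression-free assessment and the first assessment showing progression.
2. The binary rate that also counts progression first documented at the patient's 2-year assessment (months 22–26), provided that no earlier assessment in that window was progression-free.

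Take the date of the 2-year assessment into account when interpreting predictors of POD24.

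The cost is SAP wording and a small amount of extra analysis on dates already collected; no visit, scan or treatment changes. The second analysis would count a few progressions arising in months 24–26 (at most about 0.2 points under the assumptions above), and the supporting figures would probably be slightly less favourable than the primary one.

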Appendix 3 **Methods for Assessing and Recording Adverse Events**

- 3.1 Assessment of Severity of Adverse Events
- 3.2 Assessment of Causality of Adverse Events
- 3.3 Procedures for Recording Adverse Events

Appendix 3.1 Assessment of Severity of Adverse Events

The AE severity grading scale for the NCI CTCAE (v5.0) will be used for assessing AE severity. The table below will be used for assessing severity for AEs that are not specifically listed in the NCI CTCAE.

Adverse Event Severity Grading Scale

Grade	Severity
1	Mild; asymptomatic or mild symptoms; clinical or diagnostic observations only; or intervention not indicated
2	Moderate; minimal, local, or non-invasive intervention indicated; or limiting age-appropriate instrumental activities of daily living ^a
3	Severe or medically significant, but not immediately life-threatening; hospitalization or prolongation of hospitalization indicated; disabling; or limiting self-care activities of daily living ^{b, c}
4	Life-threatening consequences or urgent intervention indicated ^d
5	Death related to AE

Note: Based on the NCI CTCAE (v5.0), which can be found at:

http://ctep.cancer.gov/protocolDevelopment/electronic_applications/ctc.htm

^a Instrumental activities of daily living refer to preparing meals, shopping for groceries or clothes, using the telephone, managing money, etc.

^b Examples of self-care activities of daily living include bathing, dressing and undressing, feeding oneself, using the toilet, and taking medications, *as performed by patients who are and not bedridden*.

^c If an event is assessed as a “significant medical event,” it must be reported as an SAE (see *Section 8.1.3.1 for reporting Instructions*), per the definition of SAE in Section 8.1.1.2.

^d Grade 4 and 5 events must be reported as SAEs (see *Section 8.1.3.1 for reporting instructions*), per the definition of SAE in Section 8.1.1.2.

Appendix 3.2 Assessment of Causality of Adverse Events

For patients receiving combination therapy, causality will be assessed individually for each of the medicinal products.

Physicians should use their knowledge of the patient, the circumstances surrounding the event, and an evaluation of any potential alternative causes to determine whether or not an AE is considered to be related to the study medicine, indicating “yes” or “no” accordingly. The following guidance should be taken into consideration:

Temporal relationship of event onset to the initiation of study medicine

Course of the event, considering especially the effects of dose reduction, discontinuation of study medicine, or reintroduction of study medicine (when applicable)

Known association of the event with the study medicine or with similar treatments

Known association of the event with the disease under study

Presence of risk factors in the patient or use of concomitant medications known to increase the occurrence of the event

Presence of non-treatment-related factors that are known to be associated with the occurrence of the event

Appendix 3.3 Procedures for recording Adverse Events

Appendix 3.3.1 Infusion-Related Reactions

AEs that occur during or within 24 hours after study medicine administration and are judged to be related to studied medicinal product infusion should be captured as a diagnosis (e.g., "infusion-related reaction") in the AE section of the eCRF. If possible, avoid ambiguous terms such as "systemic reaction." Associated signs and symptoms should be recorded on the dedicated Infusion-Related Reaction eCRF. If a patient experiences both a local and systemic reaction to the same dose of studied medicinal product, each reaction should be recorded separately in the AE section of the eCRF, with signs and symptoms also recorded separately on the dedicated Infusion-Related Reaction eCRF.

Appendix 3.3.2 Diagnosis versus Signs and Symptoms

For AEs, other than infusion-related reactions (see Section 3.3.1) a diagnosis (if known) should be recorded in the AE section of the CRF rather than individual signs and symptoms (e.g., record only liver failure or hepatitis rather than jaundice, asterixis, and elevated transaminases). However, if a constellation of signs and/or symptoms cannot be medically characterized as a single diagnosis or syndrome at the time of reporting, each individual event should be recorded in the AE section of the CRF. If a diagnosis is subsequently established, all previously reported AEs based on signs and symptoms should be nullified and replaced by one AE report based on the single diagnosis, with a starting date that corresponds to the starting date of the first symptom of the eventual diagnosis.

Appendix 3.3.3 Adverse Events Occurring Secondary to Other Events

In general, AEs that are secondary to other events (e.g., cascade events or clinical sequelae) should be identified by their primary cause, with the exception of severe or serious secondary events. A medically significant secondary AE that is separated in time from the initiating event should be recorded as an independent event in the AE section of the CRF. For example:

If vomiting results in mild dehydration with no additional treatment in a healthy adult, only vomiting should be reported on the CRF.

If vomiting results in severe dehydration, both events should be reported separately on the CRF.

If a severe gastrointestinal hemorrhage leads to renal failure, both events should be reported separately on the CRF.

If dizziness leads to a fall and subsequent fracture, all three events should be reported separately on the CRF.

If neutropenia is accompanied by an infection, both events should be reported separately on the CRF.

All AEs should be recorded separately in the AE section of the CRF if it is unclear as to whether the events are associated.

Appendix 3.3.4 Persistent or Recurrent Adverse Events

A persistent AE is one that extends continuously, without resolution, between patient evaluation time points. Such events should only be recorded once in the AE section of the CRF. The initial severity (intensity or grade) of the event will be recorded at the time the event is first reported. If a persistent AE becomes more severe, the most extreme severity should also be recorded in the AE section of the CRF. If the event becomes serious, it should be reported to the marketing authorization holder immediately (i.e., no more than 24 hours after learning that the event became serious; see Section 8.1.3.1 for reporting instructions). The AE section of the CRF should be updated by changing the event from "non-serious" to "serious," providing the date that the event became serious, and completing all data fields related to SAEs.

A recurrent AE is one that resolves between patient's evaluation timepoints and subsequently recurs. Each recurrence of an AE should be recorded separately in the AE section of the CRF.

Appendix 3.3.5 Abnormal Laboratory Values

Not every laboratory abnormality qualifies as an AE. A laboratory test result must be reported as an AE if it meets any of the following criteria:

Is accompanied by clinical symptoms

Results in a change in study treatment (e.g., dosage modification, treatment interruption, or treatment discontinuation)

Results in a medical intervention (e.g., potassium supplementation for hypokalemia) or a change in concomitant therapy

Is clinically significant in the physician's judgment

Note: For oncology studies, certain abnormal values may not qualify as AEs.

It is the physician's responsibility to review all laboratory findings. Medical and scientific judgment should be exercised in deciding whether an isolated laboratory abnormality should be classified as an AE.

If a clinically significant laboratory abnormality is a sign of a disease or syndrome (e.g., alkaline phosphatase and bilirubin 5 \times the upper limit of normal [ULN] associated with cholestasis), only the diagnosis (i.e., cholestasis) should be recorded in the AE section of the eCRF.

If a clinically significant laboratory abnormality is not a sign of a disease or syndrome, the abnormality itself should be recorded in the AE section of the CRF, along with a descriptor indicating if the test result is above or below the normal range (e.g., "elevated potassium," as opposed to "abnormal potassium"). If the laboratory abnormality can be

characterized by a precise clinical term per standard definitions, the clinical term should be recorded as the AE. For example, an elevated serum potassium level of 7.0 mEq/L should be recorded as “hyperkalemia.”

Observations of the same clinically significant laboratory abnormality from visit to visit should only be recorded once in the AE section of the eCRF (see Appendix 3.3.4 for details on recording persistent AEs).

